#### 6.6 Discontinuation or Withdrawal

#### 6.6.1 Individual Participants

#### 6.6.1.1 Withdrawal from Study and Lost to Follow-up

An individual participant may withdraw from the study at any time at his/her own request (withdrawal of consent) or may be withdrawn at any time for the following reasons:

• At the request of the primary care provider if he/she thinks the study is no longer in the best interest of the participant.

- The participant is judged by the Investigator or Sponsor to be at significant risk of failing to comply with the provisions of the protocol so as to cause harm to self or seriously interfere with the validity of the study results.
- At the discretion of the Institutional Review Board (IRB)/ Ethics Committee (EC)/ or government agencies as part of their duties.

If the participant withdraws consent for disclosure of future information, the Sponsor may retain and continue to use any data/samples collected before such withdrawal of consent.

At the time of withdrawal from study all procedures scheduled for that study day plus additional assessments (not already planned for that study day) which are scheduled for the end of study drug administration (Study Day 8) or the End of Study (EOS/Day 60) visit should be completed if possible AND if the participant is agreeable. See SOE (Table 1) for data to be collected at the time of withdrawal from study.

A participant will be considered lost to follow-up if unable to be contacted by the study site. The following actions must be taken if a participant fails to present for a study required assessment:

- The site must attempt to contact the participant as soon as possible and counsel the participant on the importance of maintaining the assigned procedure schedule and ascertain whether or not the participant wishes to and/or should continue in the study.
- Before a participant is deemed lost to follow-up, the Investigator or designee must make every effort to regain contact with the participant (where possible, 3 telephone calls and, if necessary and practical, a certified letter to the participant's last known mailing address or local equivalent methods). These contact attempts should be documented in the participant's medical record.
- Should the participant continue to be unreachable, he/she will be considered to have withdrawn from the study with a primary reason of lost to follow-up.

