7.4. Efficacy Analysis for Secondary Endpoint

The secondary efficacy endpoint for Part 1 of this study is the median time (in hours) from randomization to hospital discharge (where discharge is defined as a score of 1 or 2 in the WHO Ordinal Scale for Clinical Improvement).

Kaplan-Meier curves will be constructed to display time-to- hospital discharge. Participants who are lost to follow-up or ended study early prior to achieving clinical improvement will be censored at the day of the last obtained assessment of their WHO Ordinal Scale for Clinical Improvement. Participants who complete follow-up without hospital discharge will be censored at the day of their Day 60 visit. Participants who die for any reason during the study will be right-censored at Day 60 or date of death, whichever is earlier. For the analysis of this efficacy endpoint, missing scores of the WHO Ordinal Scale for Clinical Improvement will be assumed to be > 2 (*i.e.*, no hospital discharge). Median time-to-clinical improvement and corresponding 95% confidence interval will be estimated from the Kaplan-Meier curves and tabulated for each treatment group.

The Cox proportional hazard method will be used to calculate the hospital discharge rate ratio of ANA001 relative to placebo while controlling for the stratification factors, baseline WHO Ordinal Scale for Clinical Improvement, and number of co-existing conditions. Hospital discharge rate ratio is akin to a hazard ratio but for the beneficial outcome of hospital discharge.

A hospital discharge rate ratio > 1 indicates a benefit for ANA001. Treatment groups will be compared using a stratified log-rank test.

The above analyses will be produced for all participants in the Full Analysis Set and by baseline WHO Ordinal Scale for Clinical Improvement scores. Additionally, the same analysis will be produced for participants in the Per-Protocol Analysis Set and Safety Analysis Set.

If WHO Ordinal Scale are missing at baseline, 6 hours window after first dose will be added for baseline values.

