7.5.3 Duration of COVID-19 Symptoms

Subjective symptoms assessed by the investigators to be potentially due to COVID-19, including fever, cough (productive or non-productive), sore throat, malaise, headache, muscle pain, gastrointestinal symptoms (i.e., nausea, vomiting, or diarrhea), shortness of breath (with or without exertion), and respiratory distress will be captured and followed up until resolution.

Duration (in days) to resolution of subjective COVID-19 symptoms will be defined as:

End date of last COVID-19 symptom – Start date of first COVID-19 symptom+1.

Participants who did not have resolution of COVID-19 symptoms are censored at date of completion/withdrawal. Kaplan-Meier curves will be constructed to duration of COVID-19 symptoms for participants in each treatment group. The curves will be constructed in a manner similar to the primary efficacy endpoint (Section 7.4). Median duration of COVID-19 symptoms and corresponding 95% confidence interval will be presented for each treatment group.

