7.5.8 WHO Ordinal Scale for Clinical Improvement

Number and proportion of participants who achieve a score of 1 on the WHO Ordinal Scale for Clinical Improvement on Days 8 and 15 will be tabulated by treatment group and Baseline WHO Ordinal Scale and compared in a way similar to the analysis of ICU Admissions in Section 7.5.5.

The corresponding 95% binomial confidence interval will also be reported. Sample size permitting, Wilson's method will be used to derive these confidence intervals. The difference in proportions will also be reported with the corresponding 95% confidence interval using Newcombe's method. Should the number of observed admissions be small, the exact distribution will be used instead of the normal approximation to derive the confidence intervals.

Similarly, the number and proportion of participants who achieve 2-point improvement from baseline in the WHO Ordinal Scale for Clinical Improvement on Days 8 and 15 will be analyzed based on Full Analysis Set. Median number of days to a 2-point improvement will be tabulated by treatment group and compared in a way similar to the analysis of duration of COVID-19 symptoms in Section 7.5.3. The same analysis will be provided in the Safety Analysis Set.

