7.5.11 Viral Dynamics

Observed mean and mean change in log-transformed viral load from baseline on Days 1, 4, 8, 15, and 28 will be tabulated by treatment group and compared similar to the analysis of the SOFA score in Section 7.5.6.

Time-to-viral load undetectable (*i.e.*, <LOD) by nasopharyngeal swab is defined as the number of days from randomization to achieving undetectable viral load. That is:

(Date/Time to Undetectable Nasopharyngeal Swap – Date/Time of Randomization)/24.

Participants who are lost to follow-up or ended study early prior to achieve Undetectable Nasopharyngeal Swap will be censored at the day of the last obtained assessment. Median

number of days to undetectable will be tabulated by treatment group and compared in a way similar to the analysis of duration of COVID-19 symptoms in Section 7.5.3.

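### SAP 7.5.3 gives two censoring dates for unresolved symptoms; the stated one can count unobserved time as unresolved and lengthen the median of this exploratory Part 1 endpoint

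*SAP*

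**What the plan says.** Four SAP sections bear on this, all for Part 1.

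- **7.4, time to discharge.** Participants lost or ending early before improvement "will be censored at the day of the last obtained assessment of their WHO Ordinal Scale for Clinical Improvement". Those who complete follow-up without discharge are censored at the Day 60 visit.
- **7.5.3, symptom duration.** "Participants who did not have resolution of COVID-19 symptoms are censored at date of completion/withdrawal". There is no separate rule for loss to follow-up. The paragraph then adds: "The curves will be constructed in a manner similar to the primary efficacy endpoint (Section 7.4").
- **7.5.8, time to 2-point WHO improvement.** No censoring rule is given; the endpoint is "compared in a way similar to the analysis of duration of COVID-19 symptoms in Section 7.5.3".
- **7.5.11, time to undetectable virus.** This also refers to 7.5.3 for the comparison, but states its own rule: lost participants "will be censored at the day of the last obtained assessment".

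Protocol 6.6.1.1 describes how a lost participant becomes a withdrawal. After a missed assessment the site makes repeated contact attempts, and if these fail "he/she will be considered to have withdrawn from the study with a primary reason of lost to follow-up". It does not say which calendar date is recorded. For withdrawals in general, the assessments due at that time "should be completed if possible AND if the participant is agreeable".

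**The concern.** A Kaplan-Meier estimate treats everyone as observed and event-free up to the censoring date. If that date is later than the last time anyone recorded the participant's symptoms, the participant stays in the risk set over days when resolution could have happened unseen. The denominator is too large, the curve is too high and the median can be too long.

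Symptoms can outlast discharge. Daily assessment then ends, and the scheduled visits after Day 8 are Days 15, 28 and 60, so gaps of 7, 13 and 32 days are possible. A participant seen at Day 8 with a cough, missed at Day 15 and declared lost some time later is the typical case.

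There is also a plain specification problem. Two programmers could follow 7.5.3 in good faith, one using the withdrawal date and the other the 7.4 rule, and report different medians.

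**Working it through.** **Planning figure.** The only calculable planning figure is the 374 recoveries for Part 2 (Protocol 9.1.2). With medians of 15 and 11 days, a hazard ratio of 11/15, two-sided 0.05 and 85% power:

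4 × (1.960 + 1.036)² / (ln(11/15))² = 35.91 / 0.0962 = 373.3, so 374.

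It reproduces, and this point does not touch it.

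**Inputs for the size of the effect.**
- From the documents: 30 per arm (Protocol 9.1.1), the visit days, and the 15-day placebo median. That median is borrowed as a scale only. It is a Part 2 planning value for clinical improvement, whereas 7.5.3 counts from the first symptom.
- Assumed, because the documents are silent: exponential times; 5%, 10% or 20% lost; the time of last contact; the gap from last assessment to withdrawal date.

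**Hand check.** Suppose a share d is last seen at Day 8 and censored after the median. Beyond Day 8 the estimated curve is (1 − d)·S(t) + d·S(8), where S(t) = 2^(−t/15) and S(8) = 0.691. Setting this to 0.5:

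- d = 5%: S(t) = (0.5 − 0.0345)/0.95 = 0.490, t = 15.4 days
- d = 10%: S(t) = (0.5 − 0.0691)/0.90 = 0.479, t = 15.9 days
- d = 20%: S(t) = (0.5 − 0.1382)/0.80 = 0.452, t = 17.2 days

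Censoring the same people at Day 8 returns 15.0.

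**Simulation.** The same lost participants were censored at the last assessment or at that date plus a gap. In the first two results columns, last contact is Day 1, 4, 8, 15 or 28 with equal chance. In the third, all losses are uniform up to Day 15.

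| Lost | Large-sample median; gap 2 / 7 / 14 or more days | Mean shift, 30 per arm, gap 7–28 days | Mean shift, 30 per arm, losses by Day 15, gap 7–30 days |
|---|---|---|---|
| 5% | 15.05 / 15.2 / 15.4 | +0.07 | about +0.1 to +0.6 |
| 10% | 15.1 / 15.5 / 15.9 | +0.27 to +0.34 | about +0.3 to +1.2 |
| 20% | 15.25 / 16.0 / 16.9–17.1 | +0.95 to +1.4 | about +1.1 to +2.5 (2.6 in one run) |

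The second results column takes the median as the first time the curve reaches 0.5. The third also covers the midpoint convention for a curve that sits exactly at 0.5, which accounts for most of its upper end. Later censoring never shortened a median. If every loss comes after Day 28, the shift is zero.

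**Scale.** The sampling SD of the median with 30 per arm is about 4.2 days. The shift at 10% loss is therefore 0.3/4.2 to 1.2/4.2, or 0.07 to 0.29 SD. At 20% it is 0.9/4.2 to 2.5/4.2, or 0.21 to 0.60 SD.

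**Time to 2-point improvement (7.5.8).** In Protocol Appendix 1, any discharged participant scores 1 or 2. From baseline 4 or worse, discharge is therefore already the event. Those still without it are in hospital and scored daily, including after Day 8 (Protocol Table 1 notes), so the gap is normally a day or less. A gap of weeks needs either baseline score 3, where discharge to score 2 is only one point, or a withdrawal or transfer out of observation. Exclusion criterion 1 describes score 3, so few such participants should enter, although SAP 5.2 does list a score-3 subgroup.

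**The case against.** The best defence is that 7.5.3 does not clearly impose the later date. Its reference to 7.4 can be read as importing the last-assessment rule, the protocol never defines the withdrawal date for a lost participant, and withdrawals should be assessed on the day where possible, which closes the gap. For participants who complete the study, the two rules essentially coincide. All of this stands. It makes the text ambiguous rather than plainly wrong, but it does not settle which date will be programmed.

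The cross-reference in 7.5.8 is also weaker than it looks. SAP 7.5.11 refers to 7.5.3 in much the same words and still sets its own rule, so the reference need not carry the censoring date with it. A reader might infer that the same participant is censored on two quite different dates on the same WHO scale, once for discharge and once for 2-point improvement. The documents do not support that as a material effect, because nearly everyone without a 2-point improvement is an inpatient scored daily.

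Finally, the consequence is limited. These endpoints are exploratory, Protocol 9.3 plans no formal inference in Part 1, and 7.4 already uses the preferred rule. That also stands, and it bears on priority rather than on whether to correct the text.

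**Conclusion.** The inconsistency is real, and the direction of any bias is upward. For participants lost after discharge with unresolved symptoms, the stated date in 7.5.3 can count unobserved time as unresolved. Under the assumptions above, the median lengthens by about 0.1 to 0.6 days at 5% loss, 0.3 to 1.2 at 10% and 0.9 to 2.5 at 20%, less than one sampling SD in every case. Loss rate, gap, exponential shape and the 15-day scale are all assumed.

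Two stronger readings should be resisted. One is that weeks of unobserved follow-up will be counted and the medians will be too long: that depends on losses falling before the median and on withdrawal dates recorded well after the last assessment, and the documents establish neither. The other is that the treatment comparison is distorted: 7.5.3 specifies curves, medians and confidence intervals, with no rate ratio or test, and a between-arm distortion would need assumptions about unequal loss for which the documents give no basis. The Part 1 secondary endpoint and the Part 2 sample size are unaffected. This is a modest but worthwhile correction.

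**What to change.** In SAP 7.5.3, replace the completion-or-withdrawal date with the date of the last obtained symptom assessment; this also removes the conflict with the reference to 7.4. In SAP 7.5.8, add that participants without a 2-point improvement are censored at their last obtained WHO score, as in 7.4 and 7.5.11.

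The cost is one changed phrase and one added sentence. The study already collects the assessment dates, and design, data collection and sample size stay as they are.

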7.5.4 Progression of COVID-19

The table below describes the criteria FDA adapted for severe and critical COVID-19:

| Severity | Criteria |
|----------|---|
| Severe | Development of one of the following: Symptoms suggestive of severe illness, which could include any symptom of moderate illness PLUS shortness of breath at rest or respiratory distress, OR Clinical signs indicative of severe systemic illness with COVID-19, such as respiratory rate ≥30 breaths per minute, heart rate ≥125 beats per min, SpO₂ ≤93% on room air, AND No criteria for Critical Severity |
| Critical | Evidence of critical illness, defined by at least 1 of the following: 1. Respiratory failure requiring at least 1 of the following: |

| a. Endotracheal intubation and mechanical ventilation, oxygen delivered by high flow nasal cannula (heated, humidified, oxygen delivered via reinforced nasal cannula at flow rates >20 L/min with fraction of delivered oxygen ≥0.5) |
|--|
| b. Noninvasive positive pressure ventilation (NIPPV), OR |
| c. Extracorporeal membrane oxygenation (ECMO) or clinical diagnosis of respiratory failure (i.e., clinical need for 1 of the preceding therapies, but preceding therapies not able to be administered in setting of resource limitation) |
| Shock (defined by systolic blood pressure (BP) <90 mm Hg, or diastolic BP <60 mm Hg or requiring vasopressors), OR |
| 3. Multi-organ dysfunction/failure |

The proportion of participants whose COVID-19 infection progresses to Severe or Critical at Day 15 along with the corresponding 95% binomial confidence interval will be reported by treatment group. Sample size permitting, reported binomial confidence intervals will be based on Wilson's score. Additionally, the difference in proportions will be reported along with the corresponding 95% confidence interval using Newcombe's method. Should the number of Severe or Critical COVID-19 infection be small, the exact distribution will be used instead of the normal approximation to derive the confidence intervals.

7.5.5 ICU Admission

The number and proportion of participants requiring ICU admission at any time within the first 15 days after enrollment will be tabulated by treatment group and Baseline WHO Ordinal Scale for Clinical Improvement score. The corresponding 95% binomial confidence interval will also be reported. Sample size permitting, Wilson's method will be used to derive these confidence intervals. The difference in proportions will also be reported with the corresponding 95% confidence interval using Newcombe's method. Should the number of observed admissions be small, the exact distribution will be used instead of the normal approximation to derive the confidence intervals.

Participants who did not get admitted to ICU will not contribute to this analysis

7.5.6 Sequential Organ Failure Assessment (SOFA) Score

The Sequential Organ Failure Assessment (SOFA) will be administered for all participants who get admitted to ICU. The SOFA will be scored according to authors' instructions (Appendix B.2). For participants who get discharged from ICU before Day 8 or Day 15, their last available SOFA score will be carried forward to Day 8 or Day 15, respectively.

Mean observed and mean change from baseline in SOFA score at Days 8 and 15 will be tabulated by treatment group. Additionally, the difference in the least-squares means and their standard errors adjusted for baseline SOFA score, stratification factors, WHO Ordinal Scale for Clinical Improvement score, and number of co-existing conditions will be tabulated. Corresponding 95% confidence interval of the difference between two least-squares means will also be reported.

Participants who did not get admitted to ICU will not contribute to this analysis.

7.5.7 Oxygen and Assisted Ventilation

Number and proportion of participants requiring each of the following on Days 8 and 15 will be tabulated by treatment group:

- Supplemental oxygen only: This is defined as nasal cannula and oxygen level 1-15 L/min or FiO2≤35%, or simple facemask, or non-rebreather
- High-flow nasal cannula (HFNC) oxygen: This is defined as nasal cannula and oxygen level>15L/min or FiO2>40% and up to 100%.
- Noninvasive positive pressure ventilation (NIPPV): This is defined as non-invasive CPAP or non-invasive - BIPAP
 Mechanical ventilation: This is defined as invasive – mechanical PPV, invasive – negative pressure, or invasive ECMO

Each proportion will be analyzed in a way similar to the analysis of proportion of participants requiring ICU Admission in Section 7.5.5. Additionally, the proportion of subjects requiring any of the above will also be analyzed.

Mean number of days on mechanical ventilation within 15 days after enrollment and mean number of oxygenation-free days within 15 days after enrollment will be tabulated by treatment group. Participants who are not off mechanical ventilation are censored at date of completion/withdrawal. Participants without requiring oxygenation within 15 days after enrollment are censored at Day 15 or date of completion/withdrawal, whichever is earlier.

Sample size permitting, these endpoints will be compared in a way similar to the analysis of the Duration of COVID-19 Symptoms in Section 7.5.3.

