7.5.2 Number of Days on COVID-19 Rescue Therapy

According to the protocol, participants are allowed to receive concomitant treatments during the course of the study per the standard-of-care at the investigational site. Some concomitant treatments (*e.g.*, treatments granted US FDA approval, Emergency Use Authorization or glucocorticoid therapy) may aid the cure of COVID-19. For the purpose of this analysis, medications that may have direct anti-viral effects or systemic effects on the acute inflammatory processes of the virus/COVID and are given more than 24 hours after study drug started and no more than 240 hours (10 days) after enrollment will be considered COVID-19 rescue therapy. All concomitant medications will be reviewed in a blinded fashion prior to the database lock by team members with appropriate background and training to identify concomitant treatment that may be considered COVID-19 rescue therapy.

Mean number of days on COVID-19 rescue treatment within 15 days after enrollment will be tabulated by treatment group. The difference in the least-squares mean and their standard errors adjusted for stratification factors, baseline WHO Ordinal Scale for Clinical Improvement score, and number of co-existing conditions will be tabulated. Corresponding 95% confidence interval of the difference between two least-squares means and p-value will also be reported.

Participants who do not require any COVID-19 rescue treatment during the study will be excluded from the analysis of this endpoint.

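### SAP 7.5.7 handles two 15-day counts, ventilator days and oxygenation-free days, as censored times and gives no day count for a participant who dies

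*SAP*

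**What the plan says.** SAP 7.5.7 tabulates by arm "Mean number of days on mechanical ventilation within 15 days after enrollment and mean number of oxygenation-free days within 15 days after enrollment". Both are counts in a fixed window, as in Protocol Section 3, Table 2.

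It then adds two censoring rules:

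- Ventilation: "Participants who are not off mechanical ventilation are censored at date of completion/withdrawal".
- Oxygen: "Participants without requiring oxygenation within 15 days after enrollment are censored at Day 15 or date of completion/withdrawal, whichever is earlier".

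The comparison follows another section: "Sample size permitting, these endpoints will be compared in a way similar to the analysis of the Duration of COVID-19 Symptoms in Section 7.5.3". SAP 7.5.3 builds Kaplan-Meier curves and summarises them by a median: "Median duration of COVID-19 symptoms and corresponding 95% confidence interval will be presented for each treatment group". Neither 7.5.7 nor 7.5.3 mentions death. SAP 7.5.3 refers to 7.4 for the construction of its curves. SAP 7.4, written for time to hospital discharge, right-censors a death at its date or at Day 60, whichever comes first.

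**The concern.** A count of days in a 15-day window is complete for anyone followed to Day 15. Censoring rules and a Kaplan-Meier comparison suit a time to an event, which is a different quantity. As written, the SAP names one estimand (a mean count) and compares arms on another (a median time). For oxygenation-free days it does not say what the event is.

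Death matters because ventilated patients are excluded at entry (Protocol 5.4). Ventilation therefore begins only after deterioration, when death competes with coming off the ventilator. A participant who dies inside the window is either censored, which removes the death from view, or adds a short ventilation to the mean.

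What is at stake is modest but real. The DMC reviews Part 1 efficacy and may recommend stopping for futility (Protocol 4.1). The sponsor may change Part 2 endpoints or sample size on Part 1 efficacy data (Protocol 6.6.2). Both day counts recur as exploratory endpoints in Part 2 (Protocol Table 3).

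**Working it through.** The documents give no ventilation rate, mortality or planned effect for these endpoints, so there is no figure to reproduce. All rates below are assumptions.

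**1. Named endpoint against stated rule**

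| Case | Count in 15 days | Under 7.5.7 as written |
|---|---|---|
| Never on oxygen, followed to Day 15 | 15, known | censored at Day 15 |
| On oxygen Days 1-5, free Days 6-15 | 15 − 5 = 10 | event undefined; if it is first oxygen use, it falls at the start |
| Ventilated Day 3 to end of follow-up, Day 60 | 15 − 3 + 1 = 13 | censored after 60 − 3 + 1 = 58 days |
| Dies within 15 days | no value given | no rule in 7.5.7; 7.4, if it applies, censors at death |

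The oxygen rule stops at Day 15 and the ventilation rule does not, although both endpoints use the same window.

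**2. Never-oxygen participants**

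Supplemental oxygen is only one of several ways to meet inclusion criterion 7, so some participants may never need it. Let a share p never need oxygen (value 15), and let the others have values spread evenly over 0 to 14 (mean 7; assumed). Take the count as the time, with an event for everyone who used oxygen.

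- True mean = 15p + 7(1 − p). At p = 0.2 it is 8.6; at p = 0.6 it is 11.8.
- A mean that dropped the censored participants would be 7.0 in both cases.
- At p = 0.2 the median is 14 × 0.5/0.8 = 8.75, with or without censoring.
- At p ≥ 0.5 the Kaplan-Meier median is not reached, although the true median is 15 for p > 0.5.

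**3. Death in the tabulated mean**

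Take an arm of 30 with 4 ventilated for 12 days each and 26 never ventilated (assumed).

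- No deaths: (4 × 12)/30 = 1.60 ventilator days.
- Two of the four die after 2 days: (2 × 12 + 2 × 2)/30 = 0.93, which looks better.
- Days alive and ventilator-free, death scored 0: (26 × 15 + 4 × 3)/30 = 13.4 without deaths, and (26 × 15 + 2 × 3 + 2 × 0)/30 = 13.2 with two. This ranks the arms correctly.

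**4. Death under Kaplan-Meier censoring**

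Assume exponential time to coming off the ventilator with a 7-day median, so λ = ln 2/7 = 0.099 per day. Add an independent constant death hazard h, set so that a given share die on the ventilator by Day 15. Then:

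- Raw mean ventilator days = (1 − e^(−15(h+λ)))/(h + λ).
- True probability of coming off alive by Day 15 = λ × that mean.
- Kaplan-Meier estimate with death censored = 1 − 2^(−15/7) = 0.77, whatever h is.

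| Die on ventilator by Day 15 | Raw mean days | Kaplan-Meier median | Kaplan-Meier off ventilator by Day 15 | True off ventilator, alive |
|---|---|---|---|---|
| 0% | 7.8 | 7.0 | 0.77 | 0.77 |
| 20% | 6.6 | 7.0 | 0.77 | 0.66 |
| 40% | 5.3 | 7.0 | 0.77 | 0.53 |
| 60% | 3.8 | 7.0 | 0.77 | 0.38 |

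With a 10-day median the pattern is the same: the raw mean falls from 9.3 to 5.0, the Kaplan-Meier estimate stays at 0.65, and the true figure falls from 0.65 to 0.34.

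**5. Does the raw mean always favour the arm with more deaths?**

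Assume ventilation starts on Days 2-7 and weaning comes 4-13 days later, each day equally likely, counted to Day 15. Mean ventilated days among the weaned are then 8.17. Compare fatality among the ventilated of 30% v 50%, using f × (mean if died) + (1 − f) × 8.17:

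| Death after intubation | Mean days if died | 30% fatality | 50% fatality |
|---|---|---|---|
| 1-5 days | 3.00 | 6.6 | 5.6 |
| 4-13 days | 8.17 | 8.2 | 8.2 |
| 7-13 days | 9.52 | 8.6 | 8.8 |

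The raw mean reverses the ranking only when deaths come early. Days alive and ventilator-free, with death by Day 15 scored 0, put the 30% arm ahead in all three cases.

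**The case against.** Four points can be made for the SAP.

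- **Death is not ignored.** A reader might infer that the plan has no death rule at all. That is too strong: 7.5.7 leads to 7.5.3 and then to 7.4, which censors deaths. But that rule was written for time to discharge, and step 4 shows that here it leaves the estimate unchanged however many die.
- **Early death does not shorten ventilation in the survival analysis.** A reader might infer that censored survival times make the arm with more deaths look better. The SAP does not treat death as coming off the ventilator, so under censoring the median does not move. Shortening belongs to the raw mean, and step 5 shows that it depends on when deaths occur.
- **Censoring never-oxygen participants at Day 15 does not reverse a comparison.** Nor does it bias the curve before Day 15. This stands. The harm is a known value coded as incomplete, a median that may not be reached, and a mean that could be mishandled.
- **Little rests on it.** The means are tabulated in any case, and the survival-type comparison is conditional on sample size. Deaths are reported by arm in the safety tables, and no decision rule uses these counts. If 15% were ventilated (assumed), that is 30 × 0.15 = 4.5 participants per arm, with 1.35 v 2.25 deaths at 30% v 50% fatality. This stands and keeps the severity low.

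A reader might also extend the point to rescue-treatment days in SAP 7.5.2. That section uses least-squares means with no censoring and no Kaplan-Meier step, so it does not share this defect.

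**Conclusion.** The point holds as a specification fault of low severity. The rules in SAP 7.5.7 do not estimate the mean 15-day counts that it names. A known value is censored, the ventilation rule runs past the window, the event for oxygenation-free days is undefined, and the borrowed method reports medians. These four follow from the text alone.

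Death within the window has no day-count value. If 7.4 is followed, mortality is hidden. In the tabulated mean, a death soon after intubation counts as few ventilator days. The sizes shown rest on assumed ventilation and death rates, and the direction in the raw mean depends on the timing of deaths. The documents do not support a claim that the plan will favour the arm with more deaths.

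Severity is low because these are exploratory Part 1 endpoints with 30 per arm, no formal inference is planned (Protocol 9.3), and there is no type I error adjustment (SAP 9).

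**What to change.** Reword SAP 7.5.7:

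1. Count days over Days 1-15 for every Full Analysis Set participant, with 0 ventilator days if never ventilated and 15 oxygenation-free days if never on oxygen. Do not censor anyone followed to Day 15.
2. Keep the protocol's two named means, and show deaths by Day 15 beside them.
3. Add days alive and free of ventilation, and days alive and free of oxygen, with death by Day 15 scored 0. Compare arms with a stratified rank test in place of the reference to 7.5.3.
4. State how days are assigned to a participant who withdraws alive before Day 15, with a sensitivity analysis.
5. State how days are assigned for oxygen use after discharge, with a sensitivity analysis. After Day 8, daily oxygen data are collected only in hospital and the next visit is Day 15 ± 3 days (Protocol Table 1), while score 2 of the WHO scale includes home oxygen (Protocol Appendix 1). The count is therefore not fully observed for discharged participants.

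The cost is SAP wording on data already collected. The downside is that the added measures combine death and duration in one score, which is why deaths must also be shown separately. They supplement the protocol's named endpoints and do not replace them.
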